2. HYPOTHESIS AND OBJECTIVES

2.1 Research hypothesis

Personalized AF ablation using the ‘*ablation-by-LAW*’ protocol that uses point-by-point adapted AI values according to the local MDCT-derived LAW_T, is feasible, safe and at least as effective as the current AF ablation standards.

Ablation-by-LAW involves the use of tailored point-by-point AI values according to the local MDCT-derived LAW_T, the use of a single-catheter strategy, and the integration of a MDCT-derived ‘fingerprinted’ esophagus image to modify the ablation lines aiming to avoid too close RF applications, while performing the procedures using general anesthesia and a high-rate, low-volume ventilation protocol. The following diagram constitutes a general overview of the protocol:

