2.2 Study objectives

2.2.1 Primary objective

To determine if the proposed *ablation-by-LAW* protocol is non-inferior in terms of long-term clinical outcomes when compared to other AF ablation protocols using higher AI targets, not adapted to the LAWT.

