3.11 Statistical analysis

3.11.1 Sample size

The sample size calculation has been based on the assumption that the proposed ablation protocol ('LAWT') is an acceptable alternative to the CLOSE protocol¹⁵ (non-inferiority), with the advantage of less radiofrequency applied and likely lower risk for complications. A non-inferiority margin of 10% of clinical success (arrhythmia-free survival one year after the ablation procedure) will be considered to be the largest difference that is acceptable

between both protocols for LAWT to be adopted in clinical practice. Recruiting $n = 106$ participants will be required to confer 90% power to reject the inferiority null hypothesis, that is, that the lower limit of a one-sided 95% confidence interval will be above the non-inferiority limit of -0.05 , indicating no difference between the arms. A drop-out rate of 10% is estimated, and included in the sample size calculation.

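### Section 3.11.1 labels a passed non-inferiority test as absence of a difference, but a pass excludes only a deficit larger than the margin, and there is no second arm

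*Combined protocol and SAP*

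**What the plan says.** Four places bear on this.

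- **3.11.1, margin.** The section sets "A non-inferiority margin of 10% of clinical success", which "will be considered to be the largest difference that is acceptable" between the new protocol and CLOSE.
- **3.11.1, decision rule.** The next sentence requires the "lower limit of a one-sided 95% confidence interval" to lie "above the non-inferiority limit of -0.05", and describes that outcome as "indicating no difference between the arms". No other sentence in the plan says what a pass means. Section 3.11.2 names Kaplan-Meier for the primary endpoint but does not say how the non-inferiority result is to be read.
- **2.2.1, primary objective.** This asks whether the protocol is "non-inferior in terms of long-term clinical outcomes".
- **2.1, research hypothesis.** This states that the approach "is feasible, safe and at least as effective as the current AF ablation standards". It mentions no test, margin or result.

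Section 3.1 describes a single-arm study. The comparator is the published CLOSE result, which the Introduction gives as 91.3% free of arrhythmia at 12 months.

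**The concern.** Rejecting an inferiority null supports one statement: success is not lower than the reference by more than the margin. It does not show that the difference is zero, because the interval that passes may still include a real loss of efficacy. The section itself calls the margin a difference it is prepared to accept, then describes a result that tolerates such a difference as showing none.

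This matters because the protocol trades less radiofrequency energy for efficacy that is hoped to be preserved, and 3.11.1 ties the margin to adoption in practice. A reader weighing that trade needs to know how much loss the data leave open, and the label hides that figure. The label also refers to a comparison of arms that the design does not contain.

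**Working it through.** **Inputs.** Reference success 91.3% (Introduction). Margin 10 points, or a limit of -0.05 (both 3.11.1). One-sided 95% limit (3.11.1). N = 106 with 10% dropout included, so about 106 × 0.90 = 95 evaluable (3.11.1).

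**Assumptions.** The 91.3% is fixed and known; the 1-year outcome is binary; 95 or 106 patients are evaluable. The plan names no interval method for this limit, so I show Wald, Wilson and Clopper-Pearson.

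**Step 1. The plan's own figure, 106.** With n = (z_alpha + z_beta)² p(1−p)/margin² and 90% power:
- 91.3%, margin 0.10, one-sided 5%: (1.645 + 1.282)² × 0.913 × 0.087/0.01 = 69, or 76 with dropout. Using the null variance it is 101, or 112 with dropout.
- 91.3%, limit -0.05: 273, or 303 with dropout. Null variance: 344, or 382.
- An exact match needs a success rate the section does not state: 90%, margin 0.10, one-sided 2.5% gives 95, and 95/0.90 = 106.

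So 106 is not reproduced from the stated inputs. It lies in the region of the 10% margin and far from -0.05. The sections do not settle which margin governs, so both are carried forward.

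**Step 2. Worst result that still passes.** Wald limit: p − 1.645 × √(p(1−p)/n).

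10% margin (limit must exceed 0.913 − 0.10 = 0.813):
- 83/95 = 0.8737, limit 0.8176: passes. 82/95, limit 0.8052: fails. So 12 failures pass, at 91.3 − 87.4 = 3.9 points below the reference.
- 92/106 = 0.8679, limit 0.8138: passes. 91/106, limit 0.8028: fails. So 14 failures pass, at 91.3 − 86.8 = 4.5 points below the reference.

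-0.05 limit (limit must exceed 0.863):
- 87/95 = 0.9158, limit 0.8689: passes. 86/95, limit 0.8558: fails.
- 97/106 = 0.9151, limit 0.8706: passes. 96/106, limit 0.8590: fails.
- Both passing rates are above 91.3%. Even so, the limit for 87/95 leaves a deficit of 91.3 − 86.9 = 4.4 points open.

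**Step 3. Chance of passing when the protocol is truly worse.** P(X ≥ r), with X binomial(n, true rate) and r the smallest passing number of successes. True rate is 0.863 if 5 points worse and 0.893 if 2 points worse.

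| Margin | Limit | n | r | 5 points worse | 2 points worse |
|---|---|---|---|---|---|
| 10% | Wald | 95 | 83 | 45.3% | – |
| 10% | Wald | 106 | 92 | 51.1% | – |
| 10% | Wilson | 95 | 84 | 33.6% | – |
| 10% | Wilson | 106 | 93 | 39.9% | – |
| 10% | Clopper-Pearson | 95 | 84 | 33.6% | – |
| 10% | Clopper-Pearson | 106 | 94 | 29.2% | – |
| -0.05 | Wald | 95 | 87 | 8.3% | 30.1% |
| -0.05 | Wald | 106 | 97 | 7.2% | 29.1% |
| -0.05 | Wilson or Clopper-Pearson | 95 | 88 | 4.2% | 19.0% |
| -0.05 | Wilson or Clopper-Pearson | 106 | 98 | 3.7% | 18.8% |

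Normal check for the 10% margin: Φ(0.05/SE − 1.645) with SE = √(0.863 × 0.137/n) gives 41.0% at n = 95 and 44.1% at n = 106. If the two-sided 5% level in 3.11.2 were applied instead (1.960 for 1.645), these become 29% and 32%.

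**Step 4. Loss not excluded by a bare pass.** Under the 10% margin, true failure up to 8.7 + 10 = 18.7% against 8.7%. Under -0.05, up to 8.7 + 5 = 13.7%. Neither amounts to absence of a difference.

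**The case against.** The best defence is that the plan already carries the right meaning. The same paragraph speaks of non-inferiority, names an inferiority null and defines the margin as a tolerated difference, and 2.2.1 words the objective as non-inferiority. On that view the phrase is a stray gloss inside a power statement and binds nobody's report. This stands in part: no passage dictates the wording of the final conclusion, so one cannot say that a pass will be published as equality. But the gloss is the only statement of what a pass indicates, and it contradicts the text around it.

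Two stronger readings are tempting, and the documents do not support them.

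- **That the rule as written passes a protocol 5 points worse nearly half the time.** A figure of 45% needs the 10% margin, a Wald limit, one-sided 5%, a fixed 91.3% and 95 patients. The sentence carrying the phrase sets the limit at -0.05. There, a protocol 5 points worse lies on the null boundary and passes about 4–8% of the time, and at these sizes an observed rate below 91.3% cannot pass at all.
- **That 2.1 reads a passed test as "at least as effective as the current AF ablation standards".** Section 2.1 is a hypothesis and refers to no result. The fair point is narrower: the planned test cannot establish that wording.

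**Conclusion.** The phrase in 3.11.1 is wrong as written, under both margins. A pass excludes a deficit larger than the margin and nothing more, and there is no second arm for the phrase to refer to.

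The size of what is hidden depends on an unresolved conflict. If 10% governs, a protocol truly 5 points worse passes about 29–51% of the time. If -0.05 governs, it passes about 4–8% of the time, while one truly 2 points worse passes about 19–30% of the time and true deficits of up to 5 points are not excluded. No single pass probability can be quoted until the margins are reconciled. All these figures rest on a fixed 91.3%, a binary outcome, one-sided 5% and 95 or 106 evaluable patients.

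A reader might infer that the non-inferiority test itself is invalid for this reason. That does not follow: the defect lies in the conclusion attached to the test, and correcting it changes no analysis or sample size.

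**What to change.** 1. In 3.11.1, replace the phrase with: *indicating that 1-year success is not lower than the reference rate by more than the margin*.
2. Require the success rate, its difference from the reference and the confidence interval beside any statement of non-inferiority.
3. Allow the claim in 2.1 only if the lower limit reaches the reference rate; otherwise use the non-inferiority wording of 2.2.1. With a Wald limit and 95 patients that means at most 4 failures: 91/95 gives 0.9579 − 1.645 × 0.0206 = 0.924, whereas 90/95 gives 0.9474 − 1.645 × 0.0229 = 0.910, below 0.913.
4. Reconcile the 10% margin with the -0.05 limit, and name the interval method, before quoting any pass probability.

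Items 1 to 3 cost a few lines of text and no patients or data. The downside is that the permitted claim becomes slightly weaker. Item 4 is needed in any case; if it led to a change of margin, the sample size would have to be revisited.

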3.11.2 Statistical methods

All applicable statistical tests will be 2-sided and will be performed using a 5% significance level. Continuous variables will be reported as mean \pm standard deviation, or median (range or interquartile range if data are skewed) if not normally distributed; these variables will be compared using Student's t-test if normally distributed or Mann-Whitney U test if not normally distributed. Categorical variables will be expressed as total number (percentage) and will be compared by chi-squared test. For the primary endpoint, survival free from atrial arrhythmia, we will use the Kaplan-Meier survival analysis. A multivariable Cox proportional hazards model will be performed to investigate the effects of baseline characteristics in predicting ablation results, an adjustment will also be done by recruiting center. A receiver operating curve analysis will be performed to determine optimal cutoff LAWT values for predicting AF recurrence after ablation. All efforts will be done to limit missing data on outcome. Nevertheless, missing data will be reported on the final manuscript and, as much as possible, the reasons why data are missing will be documented. If missing, a simple imputation method will be applied and reported.

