2.2.2 Secondary objectives

- To determine if the *ablation-by-LAW* approach permits to be more efficient in terms of procedure time, RF time, and fluoroscopy time.
- To evaluate the rate of complications using the *ablation-by-LAW* approach.
- To analyze the reasons for not obtaining a first-pass isolation using the *ablation-by-LAW* approach.

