3.5.2 Secondary endpoints

3.5.2.1 Acute procedural outcomes

- Procedure time (skin to skin)
- Radiofrequency time
- Number of applications (total/per RF line/per segment)
- Fluoroscopy time
- First-pass isolation rate
- Early PV reconnections

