3.6.2 Procedural evaluation

5. MDCT wall thickness variables
 - 5.1. Mean LAWV (all of the atrial measures)
 - 5.2. Mean PVI RF line WT (only around the PV line)
 - 5.3. Normalized PVI RF line WT (point thickness/maximum PVI RF line thickness)
 - 5.4. Reconnection point mean WT (mean thickness on a 3mm radius around the point)
 - 5.5. Reconnection segment mean WT (mean thickness in each segment)
 - 5.6. Coefficient of variation of wall thickness on each segment (CV-WT) standard deviation of the wall thickness/mean WT
 - 5.7. Gaussian curvature (to have an idea of the heterogeneity of tissue)
6. Procedural data of the first PVI
 - 6.1. PV anatomy (presence or absence of common vein ostia)
 - 6.2. RF time
 - 6.3. Acute reconnection sites
7. Procedural data of the re-do intervention
 - 7.1. Reconnection sites according to an 8-segment model where the antral region of the PVs is divided into segments
 - 7.2. RF time
 - 7.3. EGM attenuation time

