1. PROCEDURE AND PATIENT DATA

FIRST OPERATOR..... Anesthetist..... EVALUATING OPERATOR.....

DATE OF THE PROCEDURE..... /..... /.....

HR ventilation Yes/No Rate Tidal vol

Age: Sex: Male //Female CHA₂DS₂-VASc = HAS-BLED:... Weight Kg Height: m

CVRF: none // HBP // Dislipemia // DM-2 // Smoker // OSA // Sport (>4 h/week x 10 y)

Underlying HD: none // Hypertensive // Ischemic // HOCM // Valvular // Other

Conduction disturbances: none // LBBB // RBBB // LAHB // LPHB // Other:

Treatment: OAC: Interrupted: Yes // NO // ¿?

TEE LA Size (mm): LVEF: Mitral annulus: cm Other:

PV anatomy: 4 indep. // Left common // Right common // Accessory veins:

LAA Closure: YES // NO Closure device type and size:

2. PROCEDURAL DATA OF PVI:

Number of femoral accesses: 1 / 2 (only 2 permitted in case of ICE use)

Ablation lines adapted to fingerprinted esophagus: YES // NO (why:))

Curve of the ablation catheter (SmartTouch®): Blue // Orange // Black

Procedure time: min FAM + Merge time: min Transeptal time: min

Transeptal puncture technique: TEE // ICE

Fluoro time: sec Fluoro dose: mGy Fluoro dose (index): Gy/cm²

RF power: anterior wall W // posterior wall W

RF time: Right PV s // Left PV s

[figure not shown]
Number of RF points: Left Right

Electrical cardioversion: Yes // No

Acute complications:

Was the procedure evaluated for the absence of gaps by the 2nd operator?: YES // NO

Select at which segment/s the subjacent rhythm was (entirely or predominantly) AF/AT: This is to assess in the future whether segments where rhythm disturbances are observed could influence catheter stability, quality of RF lesions and, ultimately, be a predictor of reconnections.

[figure not shown]
Select at which segment/s **FIRST PASS** isolation was **NOT ACHIEVED**, an explain why:

.....

.....

.....

.....

[figure not shown]
Select at which segment/s **ACUTE RECONNEXION** was observed, an explain why:

.....

.....

.....

.....

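### Segment-level data are collected, but the plan states no unit of analysis and no method for several segments per patient; its listed two-group tests would be invalid if applied to segments

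*Combined protocol and SAP*

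**What the plan says.** Section 3.11.2 gives one general rule. Continuous variables are compared with the "t-test if normally distributed or Mann-Whitney U test if not normally distributed". For the rest, "Categorical variables will be expressed as total number (percentage) and will be compared by chi-squared test". The level is common to all: "All applicable statistical tests will be 2-sided and will be performed using a 5% significance level". The other named methods are Kaplan-Meier for the primary endpoint, a Cox model for ablation results and an ROC analysis for AF recurrence. The only adjustment for grouping is by recruiting center, in the sentence on the Cox model. No unit of analysis, mixed model, GEE or cluster-robust error is mentioned.

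Several variables have more than one value per patient:

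- Section 3.5.2.1 lists "Number of applications (total/per RF line/per segment").
- Section 3.6.2 lists "Reconnection segment mean WT (mean thickness in each segment"), a coefficient of variation of thickness on each segment, acute reconnection sites, and redo reconnection sites on an 8-segment model.
- The data collection sheet (Appendix 2) has the operator mark the segments where first-pass isolation failed and those where acute reconnection occurred.

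A secondary objective in section 2.2.2 is "To analyze the reasons for not obtaining a first-pass isolation".

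**The concern.** Student's t, Mann-Whitney and chi-squared tests treat every row as a separate piece of evidence. Segments of one patient share an operator, a center and, in part, a wall-thickness level: the Introduction stresses that thickness varies between patients as well as within them. If first-pass failure or reconnection also clusters by patient, a test on pooled segments uses the wrong standard error.

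The results at stake are the mechanistic ones, such as whether thicker segments, or patients with a given characteristic, are more likely to fail first-pass isolation or to reconnect. The Introduction shows how such results are used. It traces existing Ablation Index targets to a comparison of reconnected with other segments, reported with p-values of 0.002 and 0.003. Segment-level p-values from this trial could be used in the same way, so they need correct error rates.

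**Working it through.** **Inputs from the documents.** Two-sided level 5% (3.11.2). 106 patients with 10% drop-out (3.11.1), so 106 × 0.9 ≈ 95. An 8-segment model (3.6.2, redo data).

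**Assumptions, because the documents give no figure.** Segments per patient, m = 8, with m = 16 also shown because the text does not say whether 8 is per patient or per side. Outcome ICC 0.05 to 0.3. Predictor ICC 1 for a patient-level factor, and 0.5 for a variable such as wall thickness. In simulation, 10% of segments affected.

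**Step 1: the plan's own figure.** With outcome ICC 0, simulation of the three named tests (95 patients, m = 8 or 16, 2,000 runs) gives a type I error of 4.1-5.4%. The nominal 5% is reproduced when segments are independent.

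**Step 2: formula under clustering.**

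- Design effect: DE = 1 + (m − 1) × ICC(outcome) × ICC(predictor)
- Actual type I error = 2 × [1 − Φ(1.96/√DE)]

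Example with m = 8, outcome ICC 0.1 and a patient-level factor: DE = 1 + 7 × 0.1 × 1 = 1.70; 1.96/√1.70 = 1.503; type I error = 13.3%.

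For segment position balanced within patient (for example anterior against posterior), the predictor ICC is −1/(m − 1), so DE = 1 − ICC(outcome).

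**Step 3: results for m = 8.**

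| Outcome ICC | Patient-level factor: DE, error | Predictor ICC 0.5: DE, error | Balanced position: DE, error (simulated) |
|---|---|---|---|
| 0.05 | 1.35, 9.2% | 1.175, 7.1% | 0.95, 4.4% (4.6%) |
| 0.1 | 1.70, 13.3% | 1.35, 9.2% | 0.90, 3.9% (3.8%) |
| 0.2 | 2.40, 20.6% | 1.70, 13.3% | 0.80, 2.8% (2.7%) |
| 0.3 | 3.10, 26.6% | 2.05, 17.1% | 0.70, 1.9% (1.8%) |

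For m = 16 over the same outcome ICCs, a patient-level factor has DE 1.75 to 5.5 and error 13.8-40.3%. A predictor with ICC 0.5 has DE 1.375 to 3.25 and error 9.5-27.7%. If the predictor does not cluster by patient (ICC 0), DE = 1, and simulation gives 4-6%.

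**Step 4: simulation check.** Simulated t and Mann-Whitney tests agree with the formula within about 2 percentage points. Chi-squared on a dichotomised predictor is somewhat lower when the predictor ICC is below 1.

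**Step 5: does clustering by patient repair it?** A patient-cluster-robust test with 95 patients gives 4.6-6.2% in all 24 settings tried (m = 8 or 16; outcome ICC 0 to 0.3; predictor ICC 0.2, 0.5 or 1). With an illustrative redo subset of 9 patients, 30% of segments affected and predictor ICC 0.5 (all assumed), it still gives about 9%, so a small-sample method is needed there.

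**The case against.** The strongest reply is that the plan never says it will test segments. Section 3.11.2 is generic wording, and the analyses it names individually concern patient-level outcomes. The trial is single-arm, so many segment data may only be described. The objective on first-pass failure could be met by tabulating the reasons operators write on the data sheet, which has free text for this. All of that is correct. A reader might infer that segment outcomes will certainly be tested with these three tests; the documents do not establish it. What they establish is a general rule with no exception, segment-level data it could be applied to, and no stated unit of analysis.

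Three other stronger readings also go too far:

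- A reader might infer that false predictors will always appear too often. The balanced-position column shows the reverse, and predictors that do not cluster stay near 5%.
- A reader might infer that a patient-level factor in effect counts 8 or 16 times. That is the number of rows. The variance is inflated that much only if the outcome ICC is 1; here the design effects are 1.35-3.1 and 1.75-5.5.
- The data sheet's remark that segment rhythm could affect "quality of RF lesions and, ultimately, be a predictor of reconnections" might be taken as a planned analysis. The same sentence says this is to be assessed in the future.

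It also stands that the 8-segment model is stated only for the redo, and that the documents support clustering of wall thickness but give no figure for clustering of first-pass failure or reconnection.

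**Conclusion.** The gap holds in a limited form. The plan collects correlated segment-level data, names only two-group tests that assume independence, and says nothing about the unit of analysis. Applied to segments, those tests would give invalid p-values and intervals. At m = 8 and outcome ICC 0.05-0.3, they are too optimistic for patient-level factors (about 9-27% against a nominal 5%) and for predictors with ICC 0.5 (about 7-17%). They are about right for predictors that do not cluster, and too conservative for balanced segment position (about 2-5%).

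The direction follows from how the predictor varies within and between patients. The size rests on assumed ICCs and an assumed segment count for the index procedure. The affected analyses are secondary or exploratory. The primary Kaplan-Meier analysis has one outcome per patient and is unaffected. This should be settled before analysis, but it does not threaten the main result.

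**What to change.** In section 3.11.2:

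1. State the unit of analysis for each secondary outcome, and reserve the t, Mann-Whitney and chi-squared tests for variables with one row per patient.
2. For any comparison with vein, pulmonary vein pair or segment as the unit, use a mixed-effects or GEE model (logistic or linear as the outcome requires) clustered by patient, or a within-patient comparison of failed with non-failed segments. The within-patient comparison suits thickness and position; it cannot assess patient-level factors.
3. Specify a small-sample correction for the redo subset.
4. Report first-pass and reconnection rates per patient first, then per segment with cluster-robust intervals.

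The cost is protocol wording and slightly more analysis work on data already planned for collection; patient procedures do not change. Intervals widen by √DE where clustering matters. At m = 8 that is √1.35 = 1.16 to √3.1 = 1.76 times for a patient-level factor, and √1.175 = 1.08 to √2.05 = 1.43 times for a predictor with ICC 0.5. For balanced segment position they narrow, to between √0.95 = 0.97 and √0.70 = 0.84 of the naive width.

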The CLOSE study¹⁵ analyzed the utility of AI for the reduction of AF recurrences with 91.3% of the patients free from AF/AT/atrial flutter (AFL) at 12 months follow-up. The CLOSE protocol targeted an inter-lesion distance of 6 mm and AI \geq 400 at the posterior wall and \geq 550 at the anterior wall. Nonetheless, in over 40% of patients, the target AI of 400 was not attained on the posterior wall owing to chest pain and/or intraesophageal temperature rise (IQR: 378–425 AU). The same 550 and 400 AI target values were used in a retrospective study comparing AI vs. CF-guided ablation resulting in significantly lower AT/AF recurrences on the AI arm.¹³ Such targets were chosen based on a previous study that retrospectively analyzed the ablation settings at first AF ablation of patients having redo ablation. Mean AI and mean FTI being statistically lower for reconnected segments [mean AI: 395 (350–429) vs. 422 (380–464), $p=0.002$; mean FTI: 311 (225–373) vs. 371 (260–502) gs, $p=0.003$].¹²

The left atrial wall is a thin structure with heterogeneous thickness, ranging from < 1mm to > 5 mm, with an important inter and intra-patient variability.¹⁶ This variability in wall thickness is the result of a complex array of three-dimensional muscular strands.¹⁷⁻¹⁹ A prospective study already showed that first pass PVI was limited by inability to create

transmural lesions in certain anatomical sites where left atrial wall thickness (LAWT) had been described as being higher in ex-vivo hearts.^{18,20} LAWT was an independent predictor of reconnection,²¹ dormant conduction²² and AF recurrence after 12 months follow-up,²³ and it might even be a predictor of transition from paroxysmal to chronic AF.²⁴

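### The planned multivariable Cox model has no limit on covariates and no stated form of centre adjustment, while only about 8 to 9 recurrences are expected if results match the comparator

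*Combined protocol and SAP*

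**What the plan says.** Section 3.11.2 (Statistical methods) plans this: "A multivariable Cox proportional hazards model will be performed to investigate the effects of baseline characteristics in predicting ablation results". It adds that "an adjustment will also be done by recruiting center". It does not list the covariates, limit their number, give a selection rule, say how centre enters, mention penalisation or call the model exploratory. The same section sets all applicable tests at two-sided 5% and gives no multiplicity rule. Section 3.1 describes a single-arm, international, multicentre study; the number of centres is not stated.

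On size, section 3.11.1 says: "Recruiting $n = 106$ participants will be required to confer 90% power to reject the inferiority null hypothesis". It also says: "A drop-out rate of 10% is estimated, and included in the sample size calculation". No expected success rate or number of recurrences is given there. The new protocol is planned on the assumption that it "is an acceptable alternative to the CLOSE protocol". The only one-year success rate in the document is the one that the Introduction reports for the CLOSE study: "91.3% of the patients free from AF/AT/atrial flutter (AFL) at 12 months follow-up".

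**The concern.** In Cox regression, information comes from events rather than from patients. A trial of about 100 patients with a high success rate has few events, and a model with several covariates plus centre terms may ask more of them than they can give. Estimated hazard ratios can then be very large or very small by chance. If a binary covariate or a centre has no recurrences in one of its categories, the ordinary estimate for that term is infinite.

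The stake is the credibility of any published predictor of recurrence. This is the only regression model in the plan, and its stated purpose is prediction of ablation results. Because the covariates are not named in advance, a chance finding could be reported as a predictor, and a reader could not tell how many candidates had been tried.

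**Working it through.** **The plan's own figure.** The plan gives no event count to reproduce, only n = 106. With 91.3% success, a single arm against a fixed reference, one-sided 5%, 90% power and a 10-point margin:

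- Variance at the alternative: (1.645 + 1.282)² × 0.913 × 0.087 / 0.10² = 68.0, so 69; 69/0.9 gives 77.
- Null variance in the alpha term: 101; 101/0.9 gives 113.
- With the limit of -0.05 that the same section also states (variance at the alternative): 273; 273/0.9 gives 304.

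So 106 does not follow from these inputs. What follows uses only the 106, the 10% drop-out and the 91.3%, so it is not affected.

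**Expected recurrences.** Evaluable patients: 106 × 0.9 = 95.4, about 95. Events = N × (1 − success).

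| One-year success | N = 95 | N = 106 |
|---|---|---|
| 91.3% (CLOSE) | 0.087 × 95 = 8.3 (95% range 3 to 14) | 0.087 × 106 = 9.2 (4 to 15) |
| 90% (assumed) | 9.5 | 10.6 |
| 81.3% (10 points below CLOSE) | 0.187 × 95 = 17.8 (11 to 25) | 0.187 × 106 = 19.8 (12 to 28) |

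Sections 3.4.3 and 3.10.3 also exclude cases without second-operator confirmation or with a protocol violation. That can only lower these counts.

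**Precision for one covariate.** For a balanced binary covariate, SE(log HR) = √(4/events). The 95% interval runs from HR/k to HR × k, with k = exp(1.96 × SE).

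- 9 events: SE = 0.667, k = 3.7.
- 8 events: SE = 0.707, k = 4.0.
- 18 events: SE = 0.471, k = 2.5.

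With 8 to 9 events, the hazard ratio detectable with 80% power is about 6.5 to 7.3, and power for a true hazard ratio of 2 is 16 to 18%.

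**Several covariates.** Null simulation: true hazard ratio 1 throughout, exponential times, censoring at 12 months, 95 patients, ordinary Cox fit, and covariates half continuous and half binary with 30% prevalence. The numbers of covariates and centres and the dummy coding are assumptions, because the plan gives none of them. An extreme result means that at least one baseline covariate has HR > 5 or < 0.2.

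| Model | Mean events | Extreme result |
|---|---|---|
| 2 covariates, no centre terms | about 8 | about 12% |
| 3 covariates, 3 centres as dummies | about 8 | about 13% |
| 6 covariates, 5 centres as dummies | about 8 | about 39% |
| 6 covariates, 5 centres as dummies | about 18 | 7 to 9% |
| 2 covariates, Firth fit | about 8 | about 4 to 7%, none diverging |

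**Divergence in the six-covariate, five-centre model at about 8 events.** Some coefficient diverges (|log HR| > 6) in 64 to 70% of runs, but a baseline covariate does so in only 17 to 21%. The rest are centre terms.

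**Error rates in the same model.** The joint likelihood-ratio test of the six covariates rejects in about 10 to 13% of runs against a nominal 5%. Single-covariate Wald tests reject in about 5%. Multiplicity alone gives 1 − 0.95⁵ = 23% for at least one false finding among five independent 5% tests, and 1 − 0.95⁸ = 34% among eight.

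**The case against.** The strongest reply is that much of the damage depends on a model that the plan does not specify. The number of covariates, the number of centres and the form of centre adjustment are all open; stratification or a shared frailty would fit the wording as well as fixed dummies. This stands, and it is why the size is given as a range.

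Four stronger readings are tempting, and the document does not support them.

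- A reader might infer that there will be about one event or fewer per coefficient. Nine events over ten coefficients is 0.9, but the ten come from assuming six covariates and five centres.
- A reader might infer that the model will usually fail to converge. Most of that divergence is in centre dummies. Centres without a recurrence give infinite estimates only under that coding, and a diverging centre term does not by itself invalidate the covariate estimates.
- A reader might infer that the p-values in general miss the stated 5%. The joint likelihood-ratio test does in the larger model, but single-covariate Wald tests stay near 5%. Much of the remaining false-predictor risk is multiplicity, which more events would not remove.
- A reader might infer that the trial assumes 91.3%. Section 3.11.1 states no rate, and 106 is not reproduced from that figure. Section 3.5.1 also counts recurrence on symptoms alone, which could raise the number of events.

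It is also true that prediction of recurrence is neither the primary objective nor among the listed secondary objectives.

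**Conclusion.** The point holds in limited form. The plan commits to a multivariable Cox model without limiting its size, and the only success rate in the document implies about 8 to 9 recurrences. At that count even a two-covariate ordinary fit gives an extreme hazard ratio by chance in roughly one run in eight. A six-covariate model with five centre dummies does so in about two runs in five. If success were 10 points lower, with about 18 to 20 events, the same large model would give extreme estimates in 7 to 9% of runs: a smaller problem, but still too few events for an open-ended list of predictors.

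These sizes rest on the cohort matching the comparator and on the assumed covariate and centre counts. A reader might infer that the trial's main conclusion is at risk. It is not: the primary endpoint is analysed by Kaplan-Meier, separately from this model. The harm is confined to claims about predictors, so this is a worthwhile and inexpensive improvement rather than a fault in the main result.

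**What to change.** In section 3.11.2, replace the multivariable Cox sentence with wording such as: *As an exploratory analysis, a Firth-penalised Cox model will be fitted with at most two pre-named baseline covariates (for example LA diameter and pre-procedural MDCT mean wall thickness). Hazard ratios will be reported with profile-likelihood intervals and without claims of significance. Centre will be handled by stratification or by a table of recurrences by centre, not by fixed dummy variables.*

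If wall thickness is chosen, the text should say that it counts as a baseline covariate. Section 3.6.2 lists it under procedural evaluation, although the scan is done before ablation (section 3.4.1). Stating the expected number of recurrences and the success rate behind it would let a reader see why the limit is two.

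The change costs a few lines of text and a standard penalised-regression routine, with no new patients, visits or data. The downside is that fewer predictors can be examined.
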